5. LT-OLE-PEN (Period V) - long-term, open-label extension using single patient use, multi-dose, disposable pre-filled pen. Upon regulatory clearance and Sponsor's written approval, study patients should be switched to PEN. Patient will continue with their current dose. Study duration will be until marketing approval; a yearly extension request will be submitted to local EC/IRB where it is required. An updated ICF for the LT-OLE-PEN period treatment should be signed during the first PEN transition visit, prior to using the PEN or any other assessments related to the transition to PEN.

PERIOD I: SIX MONTH REPEATED DOSE (Main Study)

Following screening, eligible patients will receive their weekly doses of MOD-4023 or daily dose of r-hGH for 6 months repeated dosing including PK/PD sampling. Safety will be assessed throughout this period.

In order to introduce naïve patients to the allocated MOD-4023 dose in a gradual manner, a stepwise dose increase will be implemented. All patients randomized to receive one of the three MOD-4023 doses will start treatment for 2 weeks with the low MOD-4023 dose (0.25 mg protein/kg). Based on the patient's dose allocation, this will be followed by a dose increase to the next dose level every two weeks until the final allocated dose is reached.

OPKO Biologics	Protocol for Clinical Study CP-4-004	Page 37 of 133
Effective Date: Date of final electronic approval		

TABLE 5: DOSE INCREASE SCHEME FOR MOD-4023 COHORTS

Cohort	Dosing Scheme					
	Week 1	Week 2	Week 3	Week 4	Week 5	Week 6
Cohort I	0.25 mg protein/kg/week					
		PK/PD sampling				
Cohort II	0.25 mg protein/kg/week		0.48 mg protein/kg/week			
			PK/PD sampling			
Cohort III	0.25 mg protein/kg/week		0.48 mg protein/kg/week		0.66 mg protein/kg/week	
					PK/PD sampling	

Subsequent to the second dose administration of the targeted dose, limited (population-based) PK and PD sampling will be performed as described in visit schedules in Section 5. The proposed sampling plan is based on the following:

Selection of time points that will cover both the PK and PD absorption phase to the peak which was about 20 hours for PK and 40-60 hours for IGF-I (in the phase 2 study conducted in GHD adult patients) and having in addition time points to cover the PK elimination phase and PD return to baseline (remaining time points).

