5.8.1 Dose Modifications Based on Adverse Effects (main study)

If a patient develops a **severe GH-related adverse event** at any time during the course of the study (Main and OLE), the Sponsor, the Coordinating Investigator, the investigator or the Data Safety Monitoring Board (DSMB) may propose one of three options:

1. **If the patient is allocated to Cohort 1 (0.25 mg protein/kg/week)** the following dose will not be given. If the symptoms disappear, the patient will continue on the same dose level as initially allocated. In case the symptoms reoccur, the patient may be withdrawn from the study.
2. **If the patient is allocated to Cohort 2 (0.48 mg protein/kg/week)** the dose will be lowered to the lower dose level (0.25 mg/kg/week) for a 2-4 week period. The patient may be re-challenged, once the symptoms disappear, with the same dose level as initially allocated. In case symptoms reoccur, the patient may be kept on the reduced dose level.
3. **If the patient is allocated to Cohort 3 dose (0.66 mg protein/kg/week)** the dose will be reduced by 15% to 0.56 mg/kg/week. If the symptoms are resolved, the patient will continue on the same dose level.

In case the AE is persist or the symptoms reoccur the dose will be reduced again by 15% to 0.48 mg/kg/week. Patients, who had their dose reduced twice and who still have symptoms or they reoccur will be required to have individual medical consultation, depends on AE and /or symptoms assessment.

It is recommended to consult with study Medical Monitor prior to dose changes (the Medical Monitor must be informed of such a change after the event if prior consultation is not possible).

4. **Patient will be withdrawn from the study either:**

- Without attempt of dose reduction if such a severe AE(s) develops that may affect patient safety and wellbeing.
- If symptoms do not disappear after the transient dose interruptions or dose reductions (Please see case 1-3 above).

OPKO Biologics	Protocol for Clinical Study CP-4-004	Page 74 of 133
Effective Date: Date of final electronic approval		

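### The severe-AE dose targets in Protocol 5.8.1 are fixed to the allocated cohort and make sense only once the child is on the allocated dose; during step-up, and for some children in the OLE, the printed target contradicts the word 'reduced'

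*Protocol*

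**What the plan says.** Section 5.8.1 of the protocol covers severe GH-related adverse events. Its title names only the main study, but its text applies "at any time during the course of the study (Main and OLE", with no exception for the step-up weeks. Section 5.8 adds that dose modifications in the extension periods follow the Main Study rules.

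The action depends on allocation:

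- Cohort 2: "If the patient is allocated to Cohort 2 (0.48 mg protein/kg/week"), then "the dose will be lowered to the lower dose level (0.25 mg/kg/week) for a 2-4 week period". Re-challenge at the allocated dose is possible once symptoms have gone.
- Cohort 3: "If the patient is allocated to Cohort 3 dose (0.66 mg protein/kg/week"), then "the dose will be reduced by 15% to 0.56 mg/kg/week. If the symptoms are resolved, the patient will continue on the same dose level". If the event persists or recurs, "the dose will be reduced again by 15% to 0.48 mg/kg/week".

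Section 3 (Period I) says that every child randomised to MOD-4023 "will start treatment for 2 weeks with the low MOD-4023 dose (0.25 mg protein/kg"), rising one dose level every two weeks. Tables 2, 5 and 8 give the same scheme. Cohort 2 reaches 0.48 in week 3. Cohort 3 receives 0.48 in weeks 3-4 and 0.66 from week 5.

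Section 5.8.3 gives a second rule. It takes 15% off the most recent dose for repeated high IGF-I, and it sends severe drug-related events down a similar two-step path after discussion with the Medical Monitor and the DSMB. The note to Figure 2 says the rules also cover children on lower doses.

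**The concern.** A toxicity rule that is open at all times, but written only for the final dose, has no coherent reading for a child who is not yet on that dose or has already come off it. In Cohort 3 the text calls 0.56 a reduction when the child may be receiving 0.25 or 0.48. In Cohort 2 it lowers a child in weeks 1-2 to the dose already being given. The re-challenge clause makes the same assumption: a Cohort 2 child in weeks 1-2 has never received 0.48, so going to the allocated dose would be a first exposure at 0.48/0.25 = 1.92 times the dose at which the event occurred.

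What is at stake is that a site cannot tell from the text what to do after a severe event, and two sites could act differently under the same section. Safety and tolerability of the three doses against the comparator are part of the primary objective (Section 2.1.1), so the rule for severe events should have one reading.

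**Working it through.** **Inputs.** Targets from 5.8.1: 0.25 (Cohort 2); 0.56, then 0.48 (Cohort 3). Scheduled doses from Tables 2, 5 and 8. Reduction base from 5.8.3: 15% of the most recent dose. All doses are in mg/kg/week.

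**Step 1. Reproduce the plan's figures.** 0.66 × 0.85 = 0.561, printed as 0.56. 0.56 × 0.85 = 0.476 (or 0.66 × 0.85² = 0.477), printed as 0.48. Both figures reproduce from a starting dose of 0.66. A 15% cut from the step-up doses gives 0.25 × 0.85 = 0.2125 and 0.48 × 0.85 = 0.408. Neither is 0.56.

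**Step 2. Compare each 5.8.1 target with the scheduled dose.** Change = 100 × (target / current dose − 1).

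| Cohort and weeks | Current dose | 5.8.1 target | Ratio | Change |
|---|---|---|---|---|
| 2, weeks 1-2 | 0.25 | 0.25 | 1.00 | 0% |
| 2, week 3 onward | 0.48 | 0.25 | 0.52 | −47.9% |
| 3, weeks 1-2 | 0.25 | 0.56 | 2.24 | +124% |
| 3, weeks 3-4 | 0.48 | 0.56 | 1.17 | +16.7% |
| 3, week 5 onward | 0.66 | 0.56 | 0.85 | −15.2% |

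The second Cohort 3 target (0.48) is 92% above 0.25 and equal to 0.48, so it does not resolve the step-up weeks either.

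**Step 3. Extend to the OLE.** Under 5.8.3 a Cohort 3 child with persistently high IGF-I goes from 0.66 to 0.56 and then to 0.48. If a severe GH-related event follows, the first 5.8.1 target is again 0.56. Against 0.56 that is no change. Against 0.48 it is 0.56/0.48 = 1.17 times the current dose.

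**Step 4. Set 5.8.1 beside 5.8.3 for the same severe drug-related event.** For Cohort 3 in weeks 1-2, 5.8.1 prints 0.56 and a 15% cut from the most recent dose is 0.2125. In weeks 3-4 the figures are 0.56 and 0.408. For Cohort 2 on 0.48 they are 0.25 and 0.408. These figures show the size of the conflict only; none is proposed as a dose. Neither section gives an order of precedence.

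**The case against.** The strongest reply is that the plan has enough safeguards to prevent harm. The parties named in 5.8.1 may propose an option and are not bound to one. Consulting the Medical Monitor first is recommended, and a child can be withdrawn without any attempt at dose reduction. Section 5.8.3 already has a rule based on the most recent dose. This stands as a reason to rate the point low. It does not make the printed targets coherent: prior consultation is only recommended, and 5.8.3 gives different doses without being said to override the section written specifically for adverse events.

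Several stronger readings are tempting, and the documents do not support them.

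- *The rule orders a dose increase.* It says the dose is reduced by 15% and then prints a number that is no reduction for that child. This is a contradiction between word and number. Sections 3 and 5.8.3 provide only for decreases on safety grounds.
- *Cohort 2 is unprotected for four weeks.* Its step-up lasts two weeks, and from week 3 its rule is a real 48% cut.
- *The rule lets the next step-up go ahead.* For Cohort 2, holding 0.25 for 2-4 weeks delays the week-3 step to 0.48, so exposure falls relative to schedule. For Cohort 3, the instruction to stay on the same level points, if anything, away from a move to 0.66.
- *Severe toxicity is likely in these weeks, or the tolerability data are mislabelled.* Section 1.3 describes adverse events in children as mostly mild, and Section 7.1 has the action taken with study drug recorded for each event. Neither document shows that any child was managed under the contradictory targets.

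Timing also counts. Section 1.4.1 already reports 12-month results, and SAP Section 4.1 says 53 patients completed Period II. No step-up is described for Genotropin patients switching in the OLE. Earlier protocol versions are not available, so it is unknown whether this wording was in force when any child was stepping up.

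**Conclusion.** The contradiction is real and follows directly from the text. The Cohort 3 target exceeds the scheduled dose throughout weeks 1-4 (2.24 times, then 1.17 times). The Cohort 2 target equals the scheduled dose in weeks 1-2 only. Up to 14 children per cohort pass through these weeks. That counts children to whom the text could have applied, not children affected.

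The part that can still matter is the OLE, where a Cohort 3 child at 0.48 after two IGF-I reductions meets the same 0.56 target. That case assumes that 5.8.1 governs the event and that its Cohort 3 item is read by allocation, as written.

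Severity is minor. The Main Study step-up is finished and discretion lowers the risk, but a safety rule whose words and number disagree, and which competes with a second rule, should not stay in a protocol under which children are still being treated.

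**What to change.** Reconcile 5.8.1 with the step-up scheme (Section 3 and Tables 2, 5 and 8) and with 5.8.3, so that no dose at or above the one the child is receiving is labelled a reduction. State which of 5.8.1 and 5.8.3 governs a severe drug-related event, and align the title of 5.8.1 with its stated scope, which includes the OLE. The doses and the clinical rule are for the sponsor to decide; this point asks only that the passages agree.

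The cost is about one paragraph in 5.8.1 and a cross-reference in 5.8.3, which can go into the next amendment. It needs no extra visits, staff or data.

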5.8.2 Overdose with the Study Medication

An accidental overdose is not an AE if there are no signs or symptoms. Any undesirable medical occurrence resulting from an accidental overdose is an AE, and should be recorded and reported on the appropriate AE case report form. Since accidental overdoses with the study drug could have serious clinical consequences and/or represent a compliance issue, they should be reported immediately to [REDACTED] Safety Team [REDACTED] and evaluated by the Sponsor. The investigator should document any case of overdose and monitor the patient. Parent, or legal guardian training on adverse event reporting will be conducted at the screening visit and re-reviewed prior to patient randomization and additional retraining will be done before entering the OLE.

5.8.3 Dose adjustment paradigm

Doses may be decreased for safety reasons according to the pre-defined dose-adjustment criteria (which will be based on the severity of AEs or repeated, elevated levels of IGF-I SDS).

The dose will be decreased based on two repeated day 4(-1) levels of IGF-I $> +2.0$ Standard Deviation Score (SDS).

[figure not shown]
If a patient has an IGF-I level above +2.0 SDS, they will be requested to return for an unscheduled visit within 4-6 weeks after the $>+2.0$ SDS result, on day 4(-1) post dose. If their IGF-I level is still above +2.0 SDS, the most recent dose will be reduced by 15% (i.e. in case the starting dose is 0.66 mg/kg/week, reduction to 0.56 mg/kg/week). The patient will be treated with the new dose for at least 4 weeks before a subsequent IGF-I determination can result in a further dose modification. If the next scheduled visit is less than 4 weeks after the dose reduction was effectuated, the IGF-I result at that visit must NOT be used for additional dose recalculation. At the time of the next visit (or at an extra, unscheduled visit which complies with the 4 week minimum time period), IGF-I will be resampled. If the IGF-I is still above +2.0 SDS, the dose will be reduced an additional 15% (i.e. in case the starting dose is 0.66 mg/kg/week, reduction to 0.48 mg/kg/week). If the IGF-I is still above +2.0 SDS following 2 dose reductions (at least 4 weeks after second dose reduction), the sponsor Medical Monitor (with the assistance of the DSMB if necessary) will decide on course of treatment on an individual basis.

If AEs are defined as “severe” and drug-related, dose reduction will be introduced upon discussion with Sponsor Medical Monitor and DSMB - dose should be reduced at a similar manner as above in two step approach.

OPKO Biologics	Protocol for Clinical Study CP-4-004	Page 75 of 133
Effective Date: Date of final electronic approval		

Figure 2: Overall Dose Adjustment Scheme

This figure is an example for a dose of 0.66 mg/kg/week. The rules also applies for patients who receive lower doses.

OPKO Biologics	Protocol for Clinical Study CP-4-004	Page 76 of 133
Effective Date: Date of final electronic approval		

6. Investigational Product

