Physical examination, vital signs, AEs, local tolerability, concomitant medications, parameters of glucose metabolism (fasting glucose, insulin and HbA1C), other hormonal levels (TSH, free T4, free T3, cortisol), antigenicity (anti MOD-4023 antibodies for cohort 1-3 patients and anti r-hGH antibodies for cohort 4 patients), routine safety biochemistry and hematology, patient's height and weight, parameters of lipid metabolism, pubertal status, IGF-I and IGFBP-3 serum levels, fundoscopy.

During Period I, the dose of MOD-4023 and r-hGH will be adjusted to the patient's body weight every three months. Doses may be decreased for safety reasons according to the pre-defined dose-adjustment criteria (which will be based on the severity of AEs or elevated levels of IGF-I). For patients on MOD-4023, the dose may be decreased based on repeated day 4 levels of IGF-I above +2.0 SDS. For patients on Genotropin, the dose may be decreased based on repeated IGF-I levels above +2.0 SDS.

The study Medical Monitor shall review all AEs from entries in the e-CRF on a weekly basis and all SAE safety reports as received. The key safety data will be reviewed by an independent DSMB approximately every 6 months or on an ad-hoc basis if any safety concerns arise. After completion of Period I each patient will be assessed separately for the growth progress and overall safety. If the growth meets the pre-defined criteria¹ and there are no safety concerns, the

¹ Delta Height SDS at least 0.2

OPKO Biologics	Protocol for Clinical Study CP-4-004	Page 10 of 133
Effective Date: Date of final electronic approval		

patient will continue with the same dose, otherwise dose modifications will be performed according to the pre-determined rules.

PERIOD II: SIX MONTH CONTINUOUS DOSING PERIOD

The purpose of Period II is to collect an additional 6 months of efficacy and safety data. During period II, patients will be kept whenever it is possible on the originally allocated dose levels; however, the dose may be adjusted for safety reasons throughout the study and/or for efficacy reasons after 6 months of dosing. Patients allocated to the r-hGH dose group will continue their doses as initiated earlier, up to the end of the 12-month treatment period.

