LT-OLE starts from the 2nd year of OLE (i.e. the 3rd year of treatment in the study) until transition to PEN (LT-OLE-PEN period). Patients in Cohorts 1 and 2 entering the LT-OLE will be switched to the highest MOD-4023 dose 0.66 mg/kg/week after signing a separate informed consent (unless a different medical decision was made). In case patients from Cohorts 1 and 2 have already entered the 2nd year of OLE, the switch to 0.66 mg/kg/week will be done at their next study visit after signing a separate informed consent. Patients in Cohort 3 will continue receiving 0.66 mg/kg/week.

If the IGF-I value will be above +2.0 SDS, patients will be requested to return to the clinic within 4-6 weeks for another evaluation. If IGF-I level value will continue to be above +2.0 SDS, the dose will be reduced by 15% to 0.56 mg/kg/week. Patients with reduced dose will be required to return to the clinic within 4-6 weeks for another IGF-I evaluation. If IGF-I level value is still above 2.0 SDS, the dose will be reduced again by 15% to 0.48 mg/kg/week. Patients, who had their dose reduced twice and who still have IGF-I level above 2.0 SDS within 4-6 weeks of second dose reduction, will be required to have individual medical consultation with the Medical Monitor (with the assistance of the DSMB if necessary).

Patients who are off treatment for [REDACTED] days between the last MOD-4023 in the OLE period and the first LT-OLE dose (3rd year) will be allowed to continue into the LT-OLE period after the following samples for testing will be collected

- Parameters of glucose metabolism: fasting glucose, insulin, and HbA1c

OPKO Biologics	Protocol for Clinical Study CP-4-004	Page 12 of 133
Effective Date: Date of final electronic approval		

- Antigenicity –anti MOD-4023 antibodies
- Routine safety laboratory (biochemistry, hematology, and urinalysis)
- PD: IGF-I and IGFBP-3 baseline serum levels
- MOD-4023 baseline serum levels

During LT-OLE, all patients will be assessed once every 3 months, as specified in the Schedule of Assessment, including: auxology measurements (actual height measured on a calibrated stadiometer and body weight measurement); adjustment of dose for weight; AEs; local tolerability; concomitant medication; and dispensing of drug.

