This proposed sampling schedule was tested by simulating multiple data sets under these design conditions and all other conditions as the one of the upcoming and then fit those back using the same optimization procedures we will use after the trial. The results of that fitting procedure showed an average of only 15% in the percent error of the true simulating average PK/PD model parameters.

Patients allocated to Genotropin cohort will undergo limited PK/PD sampling after the 8th Genotropin dose (start of week 2 of dosing), as described in visit schedules (section 5).

Following the first 6 weeks of the study, all the patients will visit the hospital on a monthly basis. Patients allocated to the MOD-4023 dose cohorts (cohorts 1-3) will be monitored monthly for MOD-4023 serum levels, IGF-I and IGFBP-3 serum levels and routine safety assessments on day 4 after MOD-4023 dosing. In addition, after 5 months of dosing, patients allocated to MOD-4023 dosing will be asked to return to the medical center on the day of dosing in the morning hours prior to dosing in order to obtain a trough level MOD-4023 and PD (IGF-I and IGFBP-3) sample. Patients allocated to the Genotropin dose cohort (cohort 4) will be asked to return on any day during the relevant dosing week.

During Period I, the dose of MOD-4023 and r-hGH will be adjusted to the patient's body weight every three months. Doses may be decreased for safety reasons according to the pre-defined dose-adjustment criteria (which will be based on the severity of AEs or on repeated consecutive elevated IGF-I levels, see section 5.8). For patients on MOD-4023, the dose may be decreased based on repeated consecutive day 4 levels of IGF-I above +2.0 SDS. For patients on Genotropin, the dose may be decreased based on repeated consecutive IGF-I levels above +2.0 SDS.

OPKO Biologics	Protocol for Clinical Study CP-4-004	Page 38 of 133
Effective Date: Date of final electronic approval		

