5.3 LONG-TERM OPEN LABEL EXTENSION (LT-OLE) PERIOD IV

LT-OLE starts from the 2nd year of OLE (i.e. the 3rd year of treatment in the study) and until transition to PEN (LT-OLE-PEN period).

Patients in Cohorts 1 and 2 entering the LT-OLE will be switched to the highest MOD-4023 dose 0.66 mg/kg/week after signing a separate informed consent (unless a different medical decision was made). In case patients from Cohorts 1 and 2 who have already entered the 2nd year of OLE, the switch to 0.66 mg/kg/week will be done at their next study visit after signing a separate informed consent. Patients in Cohort 3 will continue receiving 0.66 mg/kg/week. All patients switching to 0.66 mg/kg/week will be required to attend a site visit after 3 months (on day 3 or 4 post-dosing) for the following evaluations: physical examination and vital signs, patient's height and weight, concomitant medications, glucose metabolism parameters (fasting glucose, insulin and HbA1c), antigenicity (anti MOD-4023 antibodies), routine safety laboratory (biochemistry, hematology and urinalysis), IGF-I and IGFBP-3 serum levels. In case the switch to the 0.66 mg/kg/week dose is on month 9 visit, the 3 months follow up visit will take place on dosing day. Additional visit will take place 3-4 post dosing in which only IGF-I, IGFBP-3 and MOD-4023 serum levels will be measured.

In general, if the IGF-I value will be above +2.0 SDS, please refer to section [5.8.3](#).

Patients who are off treatment for over [REDACTED] between the last MOD-4023 in the OLE period and the first LT-OLE dose (3rd year) will be allowed to continue into the LT-OLE period after the following tests and assessments will be conducted:

- Parameters of glucose metabolism: fasting glucose, insulin, and HbA1c
- Antigenicity: anti MOD-4023 antibodies
- Routine safety laboratory (biochemistry, hematology, and urinalysis)
- PD: IGF-I and IGFBP-3 baseline serum levels
- MOD-4023 baseline serum levels

The following assessments will be conducted once every 3 months (13 ±2 weeks) during LT-OLE (on day 4 (-1) post dose):

- Auxology measurements: Actual height measured on a calibrated stadiometer and body weight measurement;
- Adjustment of dose for weight;
- AEs;
- Local tolerability;
- Concomitant medication;
- Dispensing of drug and return of used drug
- Patient diary dispensing and return of completed diaries

OPKO Biologics	Protocol for Clinical Study CP-4-004	Page 60 of 133
Effective Date: Date of final electronic approval		

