The following assessments will be conducted every 6 months (± 2 weeks) on day 4 (-1) post dose on top of the 3 month assessments:

- IGF-I, IGFBP-3 and MOD-4023 serum levels.
- Once a year, patients will be required to attend another visit **on dosing day** (in addition to the semi-annual visit on day 3 or 4 post dosing) where the following additional assessments will be conducted (on top of the three and six months assessments):Anti-MOD-4023 antibodies;
- MOD- 4023 serum levels
- Physical examination;
- Vital signs;
- Parameters of glucose metabolism (fasting glucose, fasting insulin and HbA1c);
- Other hormonal levels (TSH, free T4, free T3, cortisol);
- Parameters of lipid metabolism;
- Routine safety laboratory (biochemistry, hematology and urinalysis);
- Pubertal status;
- ECG;
- Bone age;
- For males above the age of 13 - LH, FSH and testosterone. For females above the age of 12 - LH, FSH and estradiol;
- Fundoscopy (if indicated).

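### After an IGF-I dose reduction in the LT-OLE, the synopsis caps the re-test at 6 weeks, but the text of Section 5.8.3 gives only a 4-week minimum

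*Protocol*

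**What the plan says.** Two places in the protocol govern what happens after a dose is reduced for high IGF-I in Period IV.

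- **Synopsis, Period IV.** After the first 15% reduction: "Patients with reduced dose will be required to return to the clinic within 4-6 weeks for another IGF-I evaluation". A child still above +2.0 SDS "within 4-6 weeks of second dose reduction" is referred for individual consultation with the Medical Monitor. Both steps have a lower and an upper limit.
- **Section 5.8.3.** After a reduction: "The patient will be treated with the new dose for at least 4 weeks before a subsequent IGF-I determination" can lead to another change. Resampling is placed as follows: "At the time of the next visit (or at an extra, unscheduled visit which complies with the 4 week minimum time period". A scheduled visit under 4 weeks after the reduction may not be used for a further recalculation. After the second reduction the text again gives only a 4-week minimum.

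Section 5.3, the body text for the LT-OLE, does not repeat the synopsis rule. It says "In general, if the IGF-I value will be above +2.0 SDS, please refer to section" 5.8.3. The same section sets LT-OLE visits every 13 ±2 weeks.

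The two places agree on the step before the first cut: a high value is confirmed by a second sample 4-6 weeks later, and the dose is reduced only if that sample is still high. They also agree on the size of the two reductions.

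**The concern.** The same event carries a 6-week ceiling in one place and none in the text of the other, and the section that sites are told to follow is the looser one. A site that follows 5.8.3 and waits for the next scheduled visit can comply with that section and still miss the synopsis limit.

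This rule limits exposure when IGF-I is too high, and it applies while Cohorts 1 and 2 are being moved to the highest dose. How soon a child is checked after a reduction should not depend on which page the site reads.

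**Working it through.** The documents give no figure for the time to re-test under 5.8.3, so there is none to reproduce. The check is interval arithmetic on the protocol's own visit rules.

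**Inputs**
- Confirmatory sample: 4-6 weeks after the first high value (synopsis and 5.8.3).
- Re-test after each cut, synopsis: 4-6 weeks.
- Re-test after each cut, 5.8.3: at least 4 weeks. After the first cut, the next visit or an optional extra visit.
- LT-OLE visit interval: 13 ±2 weeks (Section 5.3).
- Assumptions: the first high value is found at a scheduled visit; the first cut is made at the confirmatory visit with no lag; no optional extra visit is used; the second cut is made at a scheduled visit and checked at the one after.

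**After the first cut.** Gap = visit interval minus time to confirmation.
- Nominal: 13 − 6 = 7 to 13 − 4 = 9 weeks, so 1-3 weeks past the 6-week limit.
- With windows: 11 − 6 = 5 to 15 − 4 = 11 weeks, so at most 5 weeks past it.

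**After the second cut.** Gap = one full visit interval.
- Nominal: 13 weeks, which is 13 − 6 = 7 weeks past the limit.
- With windows: 11-15 weeks, which is 5-9 weeks past it.

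**Both cuts together**

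| | First cut | Second cut | Total |
|---|---|---|---|
| Synopsis | 4-6 | 4-6 | 8-12 weeks |
| 5.8.3, scheduled visits, nominal | 7-9 | 13 | 20-22 weeks |
| 5.8.3, scheduled visits, with windows | 5-11 | 11-15 | 16-26 weeks |

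Against the synopsis maximum of 12 weeks, the nominal excess is 20 − 12 = 8 to 22 − 12 = 10 weeks. With windows it is 16 − 12 = 4 to 26 − 12 = 14 weeks.

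**Lag before the dose change.** The documents give none. If the new dose starts L weeks after the sample, each gap shortens by L, because the visit date is fixed. For L = 3 the nominal gaps become 7 − 3 = 4 to 9 − 3 = 6 weeks after the first cut, and 13 − 3 = 10 weeks after the second. The first overrun can therefore vanish; the second remains, at 10 − 6 = 4 weeks. In the other direction, a lag above 1 week can bring the earliest visit (5 weeks) below the 4-week minimum. That visit is then barred and the re-test moves to the following one.

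**The case against.** The strongest reply is that 5.8.3 is looser, not contradictory. An unscheduled visit 4-6 weeks after a cut satisfies both places, 5.8.3 offers such a visit, and Section 5.5.1 provides for unscheduled visits to follow up abnormal laboratory values. After the first cut, the nominal overrun is only 1-3 weeks. All of this stands. It does not remove the mismatch, because 5.8.3 does not require the extra visit and the synopsis does require the 4-6 week return.

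Several stronger readings are tempting, and the documents do not support them.

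- **That a child would stay above +2.0 SDS for months longer.** What is delayed is the re-test. Time above the threshold is prolonged only if the reduction did not bring IGF-I down.
- **That a site could wait for the next 6-monthly IGF-I.** Section 5.3 does schedule routine IGF-I in the LT-OLE at that interval ("The following assessments will be conducted every 6 months"), but 5.8.3 calls for resampling at the next visit after a cut, so the routine schedule does not apply.
- **That a high, normal, high sequence is handled differently.** In the LT-OLE both places reduce the dose only if the confirmatory value is still high. The differing trigger wording is mainly Period I text: "the dose may be decreased based on repeated day 4 levels of IGF-I above +2.0 SDS" in the synopsis and "the dose may be decreased based on repeated consecutive day 4 levels of IGF-I above +2.0 SDS" in Section 3.
- **That the SAP results would shift materially.** SAP 9.4 counts a patient once per 12-month period if any value exceeds 2. SAP 9.13 counts patients with an adjusted dose per period, and both rules time the first cut identically. These counts are descriptive and largely insensitive to re-test timing.

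**Conclusion.** The point holds as a gap between two statements of one safety rule. The synopsis has an upper limit of 6 weeks after each IGF-I-driven cut in the LT-OLE; the text of 5.8.3 has none. If sites rely on scheduled visits, the two re-tests take 20-22 weeks nominally instead of at most 12, about 8-10 weeks longer. Most of that arises after the second cut.

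The size rests on no lag before the dose change, no use of the optional extra visit, and a second cut made at a scheduled visit. It is a possible outcome under 5.8.3, not a forecast of what sites would do. Figure 2, which belongs to 5.8.3, is not shown, so the absence of an upper limit is established for the text only. No view is taken on which interval is right.

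**What to change.** Reconcile the synopsis text for Period IV, Section 5.3, Section 5.8.3 and Figure 2 into one rule, stated once and cross-referenced from the other places. It should give the same re-test window after the first and the second reduction, and say whether an extra visit is required when no scheduled visit falls inside that window. The sponsor and DSMB choose the values.

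As tidying only, use one term for the trigger (*repeated* or *repeated consecutive*) in the Period I text of the synopsis and in Sections 3, 5.8 and 5.8.3.

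The cost is protocol wording. No new type of procedure is needed, since 5.8.3 already provides for the extra visit.
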